1.4 Preliminary Data

This is the first study of its kind. No preliminary data is available with the use of Aggrenox in patients with COVID-19. The use of Dipyridamole in a small unpublished study from China showed better outcomes in patients with COVID-19.¹⁷

1.5 Sample Size Justification

The sample size of 132 patients (66 patients in each arm) was estimated to provide 90% power to detect a relative between-group difference of 20% reduction in composite ordinal scale (from day 0 to day 15) with assumption of mean composite ordinal scale value of 4.5 ± 1.6 (yes- this is SD) at baseline (day 0) and two-sided P value of $0.05.^{25}$ For primary efficacy, we will do an intention-to-treat analysis and include all patients who have undergone randomization and will adjust for the minimization variables. We will analyze continuous measures by means of linear regression and present as mean differences. For binary outcomes, we will present data as risk ratios from a binomial regression model.

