1.2 Research Design and Methods

1: 1 Randomized design.

Arm 1: Aggrenox plus standard care. Participants will receive Aggrenox (Dipyridamole ER 200mg/ Aspirin 25mg orally/enterally), 2 times daily (FDA–recommended dose) starting on the day of enrollment for a total of 2 weeks along with standard care.

Arm 2: Standard care. Participants will receive standard care starting on the day of enrollment for a total of 2 weeks.

We will perform a randomized, 2-arm, open-label single-site pilot study to evaluate the effect of oral Aggrenox (Dipyridamole ER 200mg/ Aspirin 25mg orally/enterally), on clinical outcomes in patients with SARS-CoV-2. In this research proposal, we will randomly assign 132 consenting participants with diagnosis of SARS-CoV-2 to two treatment groups: 1) Aggrenox (Dipyridamole ER 200mg/ Aspirin 25mg orally/enterally) + standard care and 2) standard care alone. Participants will be screened, enrolled, receive treatment and followed for 28 days. The study

Protocol Title: ATTAC-19 – Aggrenox To Treat Acute Covid-19 Pro#2020001469

Rutgers, The State University of New Jersey [name]

aim and procedure will be explained to every eligible subject and informed consent will be obtained from interested subjects or authorized proxy to participate in the study. We do not anticipate problems with enrollment as sufficient number of COVID-19 patients are admitted at Rutgers-NJMS (approximately 2-5 new COVID-19 admissions daily, and total 18-20 patients who are currently admitted at Rutgers-NJMS with 5-6 patients in intensive care units).

Randomization. The P.I. or study coordinator will review the screening and enroll participants in the randomization. Once a participant has been randomized, we will conduct all evaluations irrespective of whether the participant starts the treatment, and how long the participants continues on the treatment or not. SARS-CoV-2 patients will be allocated in a 1:1 randomized fashion using computer generated random sequence to one of two groups: the Aggrenox (Dipyridamole ER 200mg/ Aspirin 25mg orally/enterally), plus standard care or the standard care. Data collection will end after 28 days, or the patient dies or withdraws consent.

A. Research Procedures

Study Procedures:

Day 0 – Screening Visit: (Complete baseline COVID Case report form – Appendix B: Module 1)

- o Review eligibility criteria
- o Obtain informed consent for trial enrollment
- o Demographic data

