 Participants will receive Aggrenox (Dipyridamole ER 200mg/ Aspirin 25mg orally/enterally), 2 times daily (FDA–recommended dose) starting on the day of enrollment for a total of 2 weeks + standard care.
- Standard care Comparator: Participants will receive standard care starting on the day of enrollment for a total of 2 weeks.

2. Subject Enrollment

- 1. Patients who are eligible for the study will be enrolled in the clinical trial after they or their authorized proxy provide informed consent for study participation. A copy of the institution's IRB approved informed consent will be on file RedCap. The patients will be enrolled through RedCap, the Clinical Trials Management System for this study. Contact the Rutgers Clinical Trials Unit, if you have any questions about the Registration/Enrollment process.
- Registration: Any subject that has signed the consent will be entered into RedCap. A Copy of the consent will be uploaded into the Documents section.
- Enrollment: Once eligibility has been confirmed, the completed, signed and dated eligibility checklist will be uploaded into the Documents section. RedCap will randomize the patient and a sequence number (subject study ID) will be generated at the time of enrollment, this is the point the patient is considered on study.

Protocol Title: ATTAC-19 – Aggrenox To Treat Acute Covid-19 Pro#2020001469

Rutgers, The State University of New Jersey [name]

Patients will not start protocol treatment prior to registration.

3. Study Safety Assessments

The Principal Investigator is responsible for ensuring that all staff involved in the study are familiar with the content of this section.

Definitions:

Adverse Events:

An adverse event is the development of an undesirable medical condition or the deterioration of a pre-existing medical condition following or during exposure to a pharmaceutical product, whether considered causally related to the product. An undesirable medical condition can be symptoms (e.g. nausea, chest pain), signs (e.g. tachycardia, enlarged liver) or the abnormal results of an investigation (e.g. laboratory findings, electrocardiogram). In clinical studies, an AE can include an undesirable medical condition occurring at any time, including run-in or washout periods, even if no study treatment has been administered. The term AE is used to include both serious and non- serious AEs.

Serious Adverse Events:

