Change (as compared to baseline on day 0) in composite COVID ordinal scale at day 15 Ordinal scale: 1) not hospitalized with resumption of normal activities; 2) not hospitalized, but unable to resume normal activities; 3) hospitalized, not requiring oxygen; 4) hospitalized, requiring oxygen; 5) hospitalized, requiring high-flow oxygen therapy, or noninvasive ventilation; 6) hospitalized, requiring invasive ventilation; 7) ventilation plus additional organ support such as vasopressors, renal replacement therapy and ECMO and 8) death.

Secondary endpoints:

- 1) all-cause mortality assessed on day 15 and day 28.
- 2) oxygen-free days through day 28.
- 3) invasive-ventilator-free days through day 28.

Protocol Title: ATTAC-19 – Aggrenox To Treat Acute Covid-19 Pro#2020001469

Rutgers, The State University of New Jersey [name]

- 4) ICU-free days through day 28.
- 5) hospital-free days through day 28.
- 6) increase in cycle threshold (Ct) of SARS-CoV-2 PCR test as an approximation of decline in viral load at days 7 and 15.
- 7) Change in the inflammatory markers D-dimer/ ferritin/ c-reactive protein at days 7 and 15 as compared to baseline on day 0.
- 8) thromboembolic complications including stroke at day 28.
- 9) Change (as compared to baseline on day 0) in COVID ordinal scale at day 28.
- 10) if feasible urine will be analysed for markers of tubular injury IL-18, kidney injury molecule-1 [KIM-1], neutrophil gelatinase-associated lipocalin [NGAL]), inflammation (monocyte chemoattractant protein-1 [MCP-1]), and repair (human cartilage glycoprotein-40 [YKL-40]

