6.0 Data Management Plan

6.1 Data Analysis

The sample size of 132 patients (66 patients in each arm) was estimated to provide 90% power to detect a relative between-group difference of 20% reduction in composite ordinal scale (from day 0 to day 15) with assumption of mean composite ordinal scale value of 4.5 ± 1.6 (yes) at baseline (day 0) and two-sided P value of 0.05.20 For primary efficacy, we will do an intention-totreat analysis and include all patients who have undergone randomization and will adjust for the minimization variables. We will analyze continuous measures by means of linear regression and present as mean differences. For binary outcomes, we will present data as risk ratios from a binomial regression model.

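### The primary analysis adjusts for minimization variables that the plan never identifies, and the day-0 ordinal score is not named as a covariate

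*Combined protocol and SAP*

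**What the plan says.** Section 1.5 states that the primary intention-to-treat analysis will "include all patients who have undergone randomization and will adjust for the minimization variables". Section 6.1 says the same of all patients "who have undergone randomization and will adjust for the minimization variables". Neither section lists the variables.

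On allocation, section 1.2 (Research Design and Methods) says: "SARS-CoV-2 patients will be allocated in a 1:1 randomized fashion using computer generated random sequence to one of two groups". Under Subject Enrollment it adds that "RedCap will randomize the patient and a sequence number (subject study ID) will be generated at the time of enrollment". Neither statement mentions minimization, stratification or any balancing factor.

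The primary endpoint is "Change (as compared to baseline on day 0) in composite COVID ordinal scale at day 15". The only model offered for a measure of this kind is in section 1.5: "We will analyze continuous measures by means of linear regression and present as mean differences". No covariate is named there. Section 1.6 lists treatment, baseline temperature, baseline SARS-CoV test and baseline inflammatory markers as predictors. It does not link them to the primary model or call them minimization variables, and the day-0 ordinal score is not among them.

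**The concern.** The one covariate rule for the primary analysis points to factors that the plan does not contain. Either the phrase is stray or the description of randomization is incomplete, and the text does not say which. Two analysts could defend different models: no covariates, the section 1.6 list, or some other set. In an open-label trial without a fixed covariate list, that choice could be made after the data are known.

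The second half of the problem is efficiency. The endpoint is a change from day 0, so the day-0 score is collected for every patient, and it is the obvious covariate. If the minimization phrase falls away, the remaining text (linear regression, mean differences, a sample size based on a mean and an SD) most plausibly leads to an unadjusted comparison of mean change. That reading is an inference, not a rule stated in the plan. Such a test is valid under randomization, but it is generally less precise than a baseline-adjusted one and leaves part of any chance baseline imbalance in the estimate.

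**Working it through.** **Inputs from the plan (section 1.5).** Day-0 mean 4.5, day-0 SD 1.6, a 20% relative difference, 66 per arm, two-sided 0.05, 90% power. The absolute difference is not stated; I read it as 0.20 × 4.5 = 0.9 points.

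**The plan's own figure.** n per arm = 2 × [1.6 × (1.960 + 1.282) / 0.9]² = 66.4, so 67 against the stated 66. Power at 66 per arm is 89.8% by the normal approximation and 89.4% by the t test. The stated size therefore reproduces as an unadjusted two-group comparison with SD 1.6.

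**Inputs the plan does not give.** The day-15 SD (SD15) and the correlation ρ between the day-0 and day-15 scores. I use SD15 = 1.6, 2.0 and 2.4, and ρ = 0.3, 0.5 and 0.7.

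**Formulas.**
- SD of change = √(1.6² + SD15² − 2ρ × 1.6 × SD15)
- Residual SD after adjusting for day 0 = SD15 × √(1 − ρ²)
- Power from the noncentral t distribution, 0.9 points, 66 per arm

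Example (SD15 1.6, ρ 0.3): change SD = √(2.56 + 2.56 − 1.536) = 1.893; adjusted SD = 1.6 × √0.91 = 1.526.

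| SD15 | ρ | SD: change / adjusted | Power: change | Power: adjusted |
|---|---|---|---|---|
| 1.6 | 0.3 | 1.893 / 1.526 | 77.4% | 92.0% |
| 1.6 | 0.5 | 1.600 / 1.386 | 89.4% | 95.9% |
| 1.6 | 0.7 | 1.239 / 1.143 | 98.5% | 99.4% |
| 2.0 | 0.3 | 2.154 / 1.908 | 66.4% | 76.7% |
| 2.0 | 0.5 | 1.833 / 1.732 | 80.0% | 84.2% |
| 2.0 | 0.7 | 1.442 / 1.428 | 94.5% | 94.9% |
| 2.4 | 0.3 | 2.453 / 2.289 | 55.3% | 61.1% |
| 2.4 | 0.5 | 2.117 / 2.078 | 67.9% | 69.5% |
| 2.4 | 0.7 | 1.716 / 1.714 | 84.9% | 84.9% |

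**When the planned power holds.** The SD must be no more than 1.6.
- Unadjusted change needs ρ ≥ SD15 / (2 × 1.6), which is 0.50, 0.63 or 0.75 for SD15 of 1.6, 2.0 or 2.4.
- The adjusted model needs ρ ≥ √(1 − (1.6/SD15)²), which is 0, 0.60 or 0.75.

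**Chance imbalance.** The standard error of the baseline difference is 1.6 × √(2/66) = 0.279, so a difference of at least 0.5 points in either direction has probability about 7.3%. An imbalance of exactly 0.5 shifts the change estimate by (ρ × SD15/1.6 − 1) × 0.5. For ρ of 0.3 and 0.5 this is −0.35 and −0.25 (SD15 1.6), −0.31 and −0.19 (2.0), and −0.28 and −0.13 (2.4), against a target of 0.9.

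**Check on an 8-level scale.** A simulation with assumed inputs (baseline levels 3 to 7 with SD 1.25, 10% control deaths at baseline 4.5, log odds ratio 0.75, 66 per arm, 4,000 replicates, control day-15 SD about 2.4 to 2.6) gave power for change against adjusted of 54.6% vs 60.8% (ρ 0.14), 58.9% vs 60.0% (ρ 0.33) and 58.0% vs 58.4% (ρ 0.54). Type I error was 4.1% to 5.3% and 4.3% to 5.4%. The gain depends on the assumed level distribution, so take it as an order of magnitude.

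**The case against.** Four points can be made for the plan.

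- **Section 1.6 offers candidate covariates.** It does, but it neither ties them to the primary model nor calls them minimization factors. The list therefore adds another possible model instead of settling one. It does mean that a complete fix should say whether those variables enter.
- **The plan promises adjustment, so the unadjusted comparator is inferred.** This stands. If the unnamed factors include baseline severity, much of the efficiency gain is already there. The undefined covariate set does not depend on that inference; the power figures do.
- **The largest gains are the least likely.** This also stands. Patients must be hospitalized at entry, so day-0 scores lie between about 3 and 7, while day-15 scores can span 1 to 8. A day-15 SD above 1.6 is therefore more plausible than one equal to it. The gains also shrink if the day-0 SD is smaller than 1.6: with 1.25 and ρ 0.3, they are about 7, 5 and 2 points for SD15 of 1.6, 2.0 and 2.4.
- **The change-score test is valid, and the imbalance shift is not bias.** Correct: the shift is conditional on the imbalance that occurs and averages to zero over randomizations. The case for adjustment is precision and prespecification, not validity.

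One caveat applies to all of this: the appendices were not in the text available to me. If factors are listed there, they still need to be named in sections 1.5 and 6.1 and in the randomization text.

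**Conclusion.** The concern holds. The adjustment set for the primary model is undefined and does not fit the randomization described, and the day-0 ordinal score is not named as a covariate. That conclusion rests on the text alone.

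The efficiency loss is less certain. It assumes that the fallback is unadjusted change, that the target is 0.9 points, and particular values of ρ and the day-15 SD. Over ρ 0.3 to 0.5 the gain from adjustment runs from about 15 points of power down to about 2. With a wide day-15 spread, 0 to 6 points is a fair expectation. Adjustment lost no power in any closed-form or simulated scenario. This is an improvement available at almost no cost; it does not show that the planned analysis is biased or invalid.

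**What to change.** - **Reconcile the minimization phrase** in sections 1.5 and 6.1 with the randomization text. If no factors are used, delete it. If factors are used, name them in all three places.
- **Specify the primary model** in 1.5 and 6.1: linear regression of the day-15 ordinal score on treatment and the day-0 ordinal score, plus any real allocation factors, in all randomized patients, reported as the planned mean difference. State that the endpoint is unchanged: with the day-0 score in the model, the treatment coefficient is the same whether the response is the day-15 score or the change.
- **Say that the section 1.6 predictors are not in the primary model**, or list those that are.
- **Use the same model at day 28.**
- **Optionally, prespecify a baseline-adjusted proportional-odds model as supportive**, since the scale has eight ordered levels with death at the top. Making it primary would change the effect measure on which 132 was sized and would need its own power calculation.

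The cost is a few sentences in 1.5 and 6.1, one in the randomization section if factors exist, and one degree of freedom. No new data are needed, and the sample size and effect measure do not change. The text should be fixed before the outcome data are analyzed.

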1.6 Study Variables

A. Independent Variables, Interventions, or Predictor Variables

The following variables will be examined for treatment outcomes of efficacy and/or predict outcomes:

- Treatment
- Baseline temperature
- Baseline SARS-CoV test
- Baseline measure of inflammatory markers

B. Dependent Variables or Outcome Measures

The following variables will be examined for changed as result of treatment or as predictors

- Treatment Compliance
- Change in the fever curve
- Improvement in vital signs
- Time to discharge (if hospitalized)
- Adverse Events (number/percentage/grade)
- Inpatient versus Outpatient
- Change from baseline SARS-CoV test
- Change from baseline inflammatory markers

RUTGERS | eIRB APPROVED

Approval Date:

1.7 Drugs/Devices/Biologics

Generic name: Dipyridamole and Aspirin

Commercial name: Aggrenox

[figure not shown]
Aggrenox is a combination antiplatelet agent intended for oral administration. Each hard gelatin capsule contains 200 mg dipyridamole in an extended-release form and 25 mg aspirin, as an immediate- release sugar-coated tablet. In addition, each capsule contains the following inactive ingredients: acacia, aluminum stearate, colloidal silicon dioxide, corn starch, dimethicone, hypromellose, hypromellose phthalate, lactose monohydrate, methacrylic acid copolymer, microcrystalline cellulose, povidone, stearic acid, sucrose, talc, tartaric acid, titanium dioxide, and triacetin. Each capsule shell contains gelatin, red iron oxide and yellow iron oxide, titanium dioxide, and water.

Source: Commercially available

For complete information please refer to the package inserts at https://dailymed.nlm.nih.gov/dailymed/search.cfm?labeltype=all&query=aggrenox

Dipyridamole

Dipyridamole is an antiplatelet agent chemically described as 2,2',2",2"'-[(4,8-Dipiperidinopyrimido[5,4-d]pyrimidine-2,6-diyl)dinitrilo]-tetraethanol. It has the following structural formula:

C₂₄H₄₀N₈O₄ Mol. Wt. 504.63

Dipyridamole is an odorless yellow crystalline substance, having a bitter taste. It is soluble in dilute acids, methanol and chloroform, and is practically insoluble in water.

Aspirir

The antiplatelet agent aspirin (acetylsalicylic acid) is chemically known as benzoic acid, 2-(acetyloxy)-, and has the following structural formula: CgHgO4 Mol. Wt. 180.16

Protocol Title: ATTAC-19 – Aggrenox To Treat Acute Covid-19

Pro#2020001469

Protocol Version 6 Date: 4/18/2021

7/21/2021

Approval Date: Expiration Date:

Aspirin is an odorless white needle-like crystalline or powdery substance. When exposed to moisture, aspirin hydrolyzes into salicylic and acetic acids, and gives off a vinegary odor. It is highly lipid soluble and slightly soluble in water.

[figure not shown]
12 CLINICAL PHARMACOLOGY 12.1 Mechanism of Action

The antithrombotic action of AGGRENOX is the result of the additive antiplatelet effects of dipyridamole and aspirin.

Dipyridamole

Dipyridamole inhibits the uptake of adenosine into platelets, endothelial cells and erythrocytes in vitro and in vivo; the inhibition occurs in a dose-dependent manner at therapeutic concentrations $(0.5-1.9~\mu g/mL)$. This inhibition results in an increase in local concentrations of adenosine which acts on the platelet A2-receptor thereby stimulating platelet adenylate cyclase and increasing platelet cyclic-3',5'- adenosine monophosphate (cAMP) levels. Via this mechanism, platelet aggregation is inhibited in response to various stimuli such as platelet activating factor (PAF), collagen and adenosine diphosphate (ADP).

Dipyridamole inhibits phosphodiesterase (PDE) in various tissues. While the inhibition of cAMP-PDE

is weak, therapeutic levels of dipyridamole inhibit cyclic-3',5'-guanosine monophosphate-PDE (cGMP- PDE), thereby augmenting the increase in cGMP produced by EDRF (endothelium-derived relaxing factor, now identified as nitric oxide).

Aspirin

Aspirin inhibits platelet aggregation by irreversible inhibition of platelet cyclooxygenase and thus inhibits the generation of thromboxane A₂, a powerful inducer of platelet aggregation and vasoconstriction.

Pharmacodynamics

The effect of either agent on the other's inhibition of platelet reactivity has not been evaluated.

Pharmacokinetics

There are no significant interactions between aspirin and dipyridamole. The kinetics of the components are unchanged by their co-administration as AGGRENOX. Absorption

Dipyridamole:

Protocol Title: ATTAC-19 – Aggrenox To Treat Acute Covid-19 Pro#2020001469

Protocol Version 6 Date: 4/18/2021

7/21/2021

Rutgers, The State University of New Jersey [name]

Peak plasma levels of dipyridamole are achieved 2 hours (range 1–6 hours) after administration of a daily dose of 400 mg AGGRENOX (given as 200 mg BID). The peak plasma concentration at steady- state is 1.98 μ g/mL (1.01–3.99 μ g/mL) and the steady-state trough concentration is 0.53 μ g/mL (0.18– 1.01 μ g/mL).

Aspirin:

Peak plasma levels of aspirin are achieved 0.63 hours (0.5–1 hour) after administration of a 50 mg aspirin daily dose from AGGRENOX (given as 25 mg BID). The peak plasma concentration at steady- state is 319 ng/mL (175–463 ng/mL). Aspirin undergoes moderate hydrolysis to salicylic acid in the liver and the gastrointestinal wall, with 50%–75% of an administered dose reaching the systemic circulation as intact aspirin.

Effect of Food

Dipyridamole:

When AGGRENOX capsules were taken with a high fat meal, dipyridamole peak plasma levels (C_{max}) and total absorption (AUC) were decreased at steady-state by 20-30% compared to fasting. Due to the similar degree of inhibition of adenosine uptake at these plasma concentrations, this food effect is not considered clinically relevant.

Aspirin:

When AGGRENOX capsules were taken with a high fat meal, there was no difference for aspirin in AUC at steady-state, and the approximately 50% decrease in C_{max} was not considered clinically relevant based on a similar degree of cyclooxygenase inhibition comparing the fed and fasted state.

Distribution

Dipyridamole:

Dipyridamole is highly lipophilic (log P=3.71, pH=7); however, it has been shown that the drug does not cross the blood-brain barrier to any significant extent in animals. The steady-state volume of distribution of dipyridamole is about 92 L. Approximately 99% of dipyridamole is bound to plasma proteins, predominantly to alpha 1-acid glycoprotein and albumin.

Aspirin:

Aspirin is poorly bound to plasma proteins and its apparent volume of distribution is low (10 L). Its metabolite, salicylic acid, is highly bound to plasma proteins, but its binding is concentration-dependent (nonlinear). At low concentrations (<100 mcg/mL), approximately 90% of salicylic acid is bound to albumin. Salicylic acid is widely distributed to all tissues and fluids in the body, including the central nervous system, breast milk, and fetal tissues. Early signs of salicylate overdose (salicylism), including tinnitus (ringing in the ears), occur at plasma concentrations approximating 200 mcg/mL.

Metabolism and Elimination

Dipyridamole:

Dipyridamole is metabolized in the liver, primarily by conjugation with glucuronic acid, of which monoglucuronide which has low pharmacodynamic activity is the primary metabolite. In plasma,

Rutgers, The State University of New Jersey [name]

about 80% of the total amount is present as parent compound and 20% as monoglucuronide. Most of the glucuronide metabolite (about 95%) is excreted via bile into the feces, with some evidence of enterohepatic circulation. Renal excretion of parent compound is negligible and urinary excretion of the glucuronide metabolite is low (about 5%). With intravenous (i.v.) treatment of dipyridamole, a triphasic profile is obtained: a rapid alpha phase, with a half-life of about 3.4 minutes, a beta phase, with a half-life of about 39 minutes, (which, together with the alpha phase accounts for about 70% of the total area under the curve, AUC) and a prolonged elimination phase λ_Z with a half-life of about 15.5 hours. Because of the extended absorption phase of the dipyridamole component, only the terminal phase is apparent from oral treatment with AGGRENOX which was 13.6 hours.

Aspirin:

Aspirin is rapidly hydrolyzed in plasma to salicylic acid, with a half-life of 20 minutes. Plasma levels of aspirin are essentially undetectable 2–2.5 hours after dosing and peak salicylic acid concentrations occur 1 hour (range: 0.5–2 hours) after administration of aspirin. Salicylic acid is primarily conjugated in the liver to form salicyluric acid, a phenolic glucuronide, an acyl glucuronide, and a number of minor metabolites. Salicylate metabolism is saturable and total body clearance decreases at higher serum concentrations due to the limited ability of the liver to form both salicyluric acid and phenolic glucuronide. Following toxic doses (10–20 g), the plasma half-life may be increased to over 20 hours.

The elimination of acetylsalicylic acid follows first-order kinetics with AGGRENOX and has a half- life of 0.33 hours. The half-life of salicylic acid is 1.71 hours. Both values correspond well with data from the literature at lower doses which state a resultant half-life of approximately 2–3 hours. At higher doses, the elimination of salicylic acid follows zero-order kinetics (i.e., the rate of elimination is constant in relation to plasma concentration), with an apparent half-life of 6 hours or higher. Renal excretion of unchanged drug depends upon urinary pH. As urinary pH rises above 6.5, the renal clearance of free salicylate increases from <5% to >80%. Alkalinization of the urine is a key concept in the management of salicylate overdose [see Overdosage (10)]. Following therapeutic doses, about 10% is excreted as salicylic acid and 75% as salicyluric acid, as the phenolic and acyl glucuronides, in urine.

Specific Populations Geriatric Patients:

Dipyridamole:

In ESPS2 [see Clinical Studies (14)], plasma concentrations (determined as AUC) of dipyridamole in healthy elderly subjects (>65 years) were about 40% higher than in subjects younger than 55 years receiving treatment with AGGRENOX.

Hepatic Dysfunction:

No study has been conducted with AGGRENOX in patients with hepatic dysfunction.

Dipyridamole:

In a study conducted with an intravenous formulation of dipyridamole, patients with mild to severe hepatic insufficiency showed no change in plasma concentrations of dipyridamole but showed an increase in the pharmacologically inactive monoglucuronide metabolite. Dipyridamole can be dosed without restriction as long as there is no evidence of hepatic failure.

RUTGERS

THE STATE UNIVERSITY
OF NEW LEDGEF

Rutgers, The State University of New Jersey [name]

Aspirin:

Avoid aspirin in patients with severe hepatic insufficiency.

Renal Dysfunction:

Dipyridamole:

In ESPS2 patients [see Clinical Studies (14)], with creatinine clearances ranging from about 15 mL/min to >100 mL/min, no changes were observed in the pharmacokinetics of dipyridamole or its glucuronide metabolite if data were corrected for differences in age.

Aspirin:

Avoid aspirin in patients with severe renal failure (glomerular filtration rate <10 mL/min). Drug Interaction Studies

A dedicated drug interaction study was conducted in 60 healthy volunteers to evaluate the effects of omeprazole 80 mg administered once daily on the pharmacokinetics (PK) of dipyridamole and the pharmacodynamics (PD) of acetylsalicylic acid when co-administered with AGGRENOX twice daily. Dipyridamole exposure (C_{max} and AUC) at steady-state were similar with or without omeprazole co- administration. The pharmacokinetics of acetylsalicylic acid was not characterized. However, the antiplatelet activity as measured by arachidonic acid induced platelet aggregation was similar between the treatment arms at steady-state.

NONCLINICAL TOXICOLOGY

Carcinogenesis, Mutagenesis, Impairment of Fertility

In studies in which dipyridamole was administered in the feed to mice (up to 111 weeks in males and females) and rats (up to 128 weeks in males and up to 142 weeks in females), there was no evidence of drug-related carcinogenesis. The highest dose administered in these studies (75 mg/kg/day) was, on a 2 mg/m basis, about equivalent to the maximum recommended daily human oral dose(MRHD) in mice and about twice the MRHD in rats.

Combinations of dipyridamole and aspirin (1:5 ratio) tested negative in the Ames test, in vivo chromosome aberration tests (in mice and hamsters), oral micronucleus tests (in mice and hamsters) and oral dominant lethal test (in mice). Aspirin, alone, induced chromosome aberrations in cultured human fibroblasts. Mutagenicity tests of dipyridamole alone with bacterial and mammalian cell systems were negative.

Combinations of dipyridamole and aspirin have not been evaluated for effects on fertility and reproductive performance. There was no evidence of impaired fertility when dipyridamole was administered to male and female rats at oral doses up to 500 mg/kg/day (about 12 times the MRHD on a mg/m2 basis). A significant reduction in number of corpora lutea with consequent reduction in implantations and live fetuses was, however, observed at 1250 mg/kg (more than 30 times the MRHD on a mg/m2 basis). Aspirin inhibits ovulation in rats.

A. Drug/Device Accountability and Storage Methods

Drug accountability logs and pharmacy records must be maintained at the hospital pharmacy and must be available for review upon request. Drug accountability logs and pharmacy records

Rutgers, The State University of New Jersey [name]

will be reviewed during monitoring visits and by the Research Pharmacy Shared Resource of Rutgers Cancer Institute of New Jersey.

B. Treatment Compliance

The study medication will be given in accordance with the protocol and the instructions of the treating investigator. For those subjects who will be discharged from the hospital before 14 days, the study drugs will be provided to patients to be self-administered together with the current Aggrenox product information. They will be requested to keep pill diary. During the telephone visits with the patients every 3rd day after discharge, the patients will be enquired about their compliance with the medications. A pill diary will be provided and must be completed by the patient to document treatment course.

